### 4.2 Blinding

Given the nature of the intervention, blinding of participants, study team or analysts is not feasible.

## 5 Methods: Data collection, management, and analysis

### 5.1 Data collection methods

There will be three modes of data collection used in this study

- i) Direct data collection by fieldworkers for the recruitment of the primary distributors.

- ii) Telephone-based data collection by the central helpline staff for all follow-up data and enrolment of peers
- iii) Central data entry of information data on kit packaging labels

Data collection will be carried out by trained research assistants on password protected tablets and smartphones which are tracked via an asset register. These devices will be collected from the Data Management team at the start of the day and returned at the end of the day to be stored in a locked room. Data will be entered using Open Data Kit installed on tablets and smartphones and will be transferred to the electronic database on a daily basis. Following confirmation of successful data transfer, records will be deleted from the smartphones and tablets at the end of each day, in order to minimise the amount of data stored on these devices.

All data will be entered into a central database and used for study monitoring and analysis.

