- iv. After seven days the helpdesk will contact the distributor and the intended recipients to ascertain whether kits have been received and used, to collect behavioural HIV risk data for the recipients and encourage attendance at a healthcare facility for a confirmatory test. HIVST recipients will be invited to complete the informed consent over the telephone and be enrolled in the study. Follow-up calls will be made to these individuals if necessary. Recipients will be encouraged to consider becoming distributors and advised on the location of community facilities (shops, pharmacies, hairdressers etc.) from where they can obtain the HIVST packs for distribution. This method of HIVST distribution through community-based hubs has been proven to be successful in studies in other Sub-Saharan African settings. [48] A small renumeration of \$1 per peer will be transferred electronically to the initial distributor for each kit successfully distributed. Successful distribution to peers is defined as the peer having received the HIVST and has been successfully contacted by the helpline to confirm receipt of the HIVST but does not have to use the HIVST or agree to enrol in the study as a distributor. Names and cell numbers will be collected for intended recipients by the study team and held confidentially.

- v. If the recipient chooses to become a distributor they will go to the facility and the owner will check using a real-time database that they have not already received a pack of kits for distribution. If they pass this screening, they will be given a pack of three HIVST kits for within cluster distribution, again A small renumeration will be paid to the facility owner for each pack of kits given out.
- vi. After seven days the helpdesk will contact the second level recipients and steps iv) and v) will be repeated until all kits allocated to a particular community have been distributed.
- vii. When participants attend a clinic for confirmatory testing, they will return the HIV test kit packaging with the unique label and based on their self-reported HIVST result (unreactive/reactive) be screened for PrEP or ART. The outcome of the screening will be recorded in a tick-box on the label and the packaging deposited in a secure box at the clinic from where it will be collected by the study team.

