- viii. HIVST kits will be returned to the central data processing facility for data entry and an additional small renumeration of \$1 paid to the initial distributor for each individual attending the clinic and participating in a confirmatory HIV test.
- ix. All individuals initiating PrEP or ART will be contacted monthly for six months to provide support and to ascertain whether they are still adhering to/continuing with PrEP/ART.
- x. Additionally, we will contact all men who report they are still taking PrEP/ART at the end of the follow-up period in order to obtain a dry blood spot to verify the self-report of adherence. This will be sent for analysis in order to assess the intracellular levels of tenofovir diphosphate (TFV-DP) in red blood cells . [49]

In a second phase of the intervention, we will return to the intervention clusters and invite the initial distributors to participate in a second phase of wider distribution. In this stage they will be able to distribute the packs of kits to individuals they contact over the next 14 days resident anywhere within the study site. The distribution process will proceed as previously for up to 2 months following the initial acceptance of the HIVST pack.

[figure not shown]

Figure 2 Schematic flowchart for the intervention as described in steps i) to x) above

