### **3.3.2 Control – Standard of care**

The existing Ministry of Health and Child Care programme of direct HIVST distribution in the community through community health workers (CHW) will be the standard of care in the study.

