### **3.3.6 HIVST packaging and kit inserts**

Study specific packaging will be created for each HIVST kit into which the original kit with packaging from the manufacturer will be inserted. A sticker on each box will contain the following information:

- A unique 6-digit identifier for the kit
- A set of tick-boxes on which the clinic staff will record the outcome of the engagement with the clinic
- A kit insert sheet within each box will contain the following:
  - A copy of the informed consent form
  - Details of accessing SMS-based HIV risk self-assessment tool
  - Contact details for the study helpline
  - Details of the study procedures including the renumerations paid for successful kit distribution and engagement of recipients with the primary care clinics

- Detailed instructions on the use and interpretation of the HIVST kit

Individual HIVST kits will be placed in a larger box with its own unique identifier. Four kits will be provided in these boxes for the primary distributors and three for the secondary distributors. The study team will keep a record of the unique identifiers of the kits packaged in each box to enable the kit distribution process to be tracked.

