## **3.4 Outcomes**

**The primary outcome** of the trial will be the proportion of men initiating PrEP out of all men aged 18 and over.

**Secondary outcomes will include:** i) the proportion of men self-testing for HIV over the period of the intervention out of all men aged 18 and over. and ii) the proportion of screened men adhering to PrEP or ART six months after initiation, measured by laboratory analysis of dry blood spots, out of all men initiating PrEP or ART after receiving an HIVST kit.

The qualitative performance evaluation will inform work to combine several quantitative data sources to evaluate how the intervention spread through social networks, and how network position and structure affected trial outcomes. We will combine information on intended and actual HIVST recipients with the existing Manicaland census data to measure what proportion of PrEP/ART eligible men were reached by our intervention. We will assess the level of network saturation achieved by the distribution process [16], and whether our approach reached individuals at higher risk of HIV acquisition as the recruitment process advanced – a key aim of the respondent driven sampling (RDS) methods on which our peer recruitment methods are based. Using entity resolution algorithms and hand-checking, we will identify linkages across distribution chains, and from this build network graphs of connections between men in the study areas. We will use these graphs to describe the structure of local male peer networks and statistically evaluate how characteristics of distributors and their social contacts influenced network distribution process and subsequent engagement with care. We will also evaluate whether intervention success differed across study clusters based on cluster-level network structures (e.g., density, clustering, age, and risk homophily) as well as by non-network characteristics (e.g., urbanicity, economy). Finally, once wider geographic distribution occurs in the second trial phase, we will evaluate whether distribution chains overlap and if greater geographical distribution affects study outcomes. We expect that our work will explain variation in outcomes and detail the contextual factors to consider when replicating or taking this intervention to scale. [33] We also expect to develop light-touch tools for use by implementors pre- and during implementation of such interventions, which can guide localization of this socially mediated design.

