### 3.5 Participant timeline

The follow-up schedule for recipients of HIVST kits is shown in figure 4.

[figure not shown]

Figure 4 Timeline for engagement with participants after HIVST kit distribution

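### PrEP initiation is captured only through the intervention pathway; no source is named for control clusters, and the primary comparison needs one source common to both arms

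*Protocol*

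**What the plan says.** Section 3.4 defines the primary outcome as "the proportion of men initiating PrEP out of all men aged 18 and over". The first secondary outcome, self-testing, has the same denominator. Section 5.3 compares the arms by intention to treat across all randomised clusters.

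The routes by which an initiation could reach the study database are these:

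- **Kit labels.** At the clinic, step vii of section 3.3.1 states: "The outcome of the screening will be recorded in a tick-box on the label". Section 5.1 then lists "Central data entry of information data on kit packaging labels". Section 3.3.6 says who receives the labelled kits: "Four kits will be provided in these boxes for the primary distributors and three for the secondary distributors".
- **Helpline calls.** Section 5.1 lists "Telephone-based data collection by the central helpline staff for all follow-up data and enrolment of peers". In section 3.3.1 these calls go to distributors and intended recipients. Step ix adds: "All individuals initiating PrEP or ART will be contacted monthly for six months". Section 3.5 says: "The follow-up schedule for recipients of HIVST kits is shown in figure 4".
- **Fieldworkers.** The remaining mode in section 5.1 is recruitment of the primary distributors.

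Section 3.3.2 covers the control arm in one sentence: the Ministry "programme of direct HIVST distribution in the community through community health workers (CHW) will be the standard of care". It describes no data collection there.

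**The concern.** The three modes in section 5.1 follow the intervention from distributor to recipient to clinic. A man in a control cluster has no study kit, no label to return and no described helpline contact, so none of these modes would record him starting PrEP. A man in an intervention cluster who starts PrEP without a study kit would also miss the label route.

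This is the numerator of the primary comparison. There are three possibilities. If only the described modes are used, control initiations are not counted. If control men are counted from some other source while intervention men are counted from labels and calls, any difference in completeness between the sources enters the effect estimate. If one source serves both arms, that difference between sources disappears. The protocol does not say which applies. Section 4.2 states that blinding of participants, study team and analysts is not feasible, so blinding offers no protection against unequal ascertainment.

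**Working it through.** **1. Could another passage supply the control count?**

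- Section 5.1 is not a full list of the study's data: dried blood spots (3.3.1, step x), SMS risk responses (3.3.3) and qualitative data (3.3.8) lie outside it. It therefore does not prove that no other source will be used.
- The Manicaland surveillance and census could cover both arms. They appear as infrastructure (2.1.1), background data for the prevention cascade (2.1.2), cluster boundaries (2.3), the recruitment cohort (3.1), a denominator for reach (3.4), sample-size input (3.6) and a precedent for telephone consent (7.3). None of these makes them the source of trial-period PrEP initiations.
- Section 5.2 mentions survey data and section 5.3 mentions baseline data. Neither specifies an outcome survey in both arms. The legible rows of the timeline in section 3.8 show none.

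No passage names a control-arm source for PrEP initiation or for self-testing.

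**2. The plan's own figures (section 3.6).**

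- Intervention: 90 × 0.70 × 0.80 × 0.33 × 0.43 = 7.15 per cluster; × 22 = 157; 157 / 1,795.5 = 8.8%.
- Control: 3,591 / 2 × 0.02 = 35.9, about 36 initiations.
- Ratio: 8.8 / 2 = 4.4.
- Power: effective n per arm = 22 × 81 / [1 + 80 × 0.1] = 1,782 / 9 = 198. Standard error = √[(0.02 × 0.98 + 0.088 × 0.912) / 198] = 0.0225. Then 0.068 / 0.0225 − 1.96 ≈ 1.07, a power of 85.7% (85.2% with pooled null variance). This assumes a two-sided 5% test. The stated figure of more than 85% is reproduced and is not in dispute.

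The 8.8% is built only from kit recipients, while the 2% is projected usage in control communities. The two planning rates already rest on different bases.

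**3. Effect of unequal capture.** Let s_I and s_C be the fractions of true initiations captured in the intervention and control arms. Then observed ratio = 4.4 × s_I / s_C. Every pair below is assumed, because the protocol gives none.

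The rejection rates come from a beta-binomial simulation: 22 clusters of 82 men per arm, ICC 0.1, 40,000 runs, pooled cluster-level t-test at 5%, events thinned at random. Type I error uses 2% in both arms; power uses 8.8% against 2%.

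| s_I, s_C | Observed ratio | Type I error | Power |
|---|---|---|---|
| 1, 1 | 4.4 | 3.7% | 88% |
| 1, 0.75 (9 control events missed) | 5.9 | 4.6% | – |
| 1, 0.5 (18 missed) | 8.8 | 9.0% | – |
| 0.9, 1 | 4.0 | – | 83% |
| 0.75, 1 | 3.3 | 4.8% | 73% |
| 0.5, 1 | 2.2 | 8.6% | 45% |
| 0.5, 0.5 | 4.4 | – | 85% |

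Of the 8.6% at (0.5, 1), only 0.2 points favour the intervention.

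Random thinning lowers the observed ICC, to about 0.05 at 50% capture. With the ICC held at 0.1 for the captured events, type I error is 5.3% at (1, 0.75) and 12.1% at (1, 0.5). Power is then 82%, 66% and 29% at (0.9, 1), (0.75, 1) and (0.5, 1), and about 63% at (0.5, 0.5).

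On the literal reading, with nothing captured in control (1, 0), the simulated false-positive rate is about 69%.

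**The case against.** The strongest reply is that this argues from silence. Section 5.1 is not exhaustive, two figures that might bear on data flow (Figures 2 and 4) are not reproduced in the text reviewed, and a statistical analysis plan that was not seen may define how the outcome is derived. The capture fractions are invented, and the cluster-level t-test is not the planned random-effects Poisson model. Even with a quarter of control events missed, type I error stays near nominal (4.6%, or 5.3% with the ICC held). A common source that is incomplete would itself cost power.

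Part of this stands. The protocol does not show that bias will occur, the illustration gives scale rather than a prediction, and the possible power loss under a common source must be acknowledged.

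It does not remove the point. An analysis plan can define how collected data are used, but it cannot create data that were never collected in control clusters. That collection needs field procedures and possibly ethics approval, so it belongs in the protocol's data collection section. That section exists and describes only the intervention pathway. Nor is asking for a kit-independent source merely a preference: no labelled study kits are described for control men, so a kit-based source cannot be common to both arms.

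**Conclusion.** The concern holds and must be fixed before the primary comparison can be interpreted. The protocol requires PrEP initiation among all men in 44 clusters but describes its capture only along the intervention pathway. It neither names a source for control clusters nor says that both arms share one. The same gap affects self-testing.

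Confidence in the omission is high. Whether bias follows, how much and in which direction depend on the source finally used. With only about 36 control events expected, modest gaps move the estimate: missing 9 shifts the ratio from 4.4 to 5.9. Type I error rises materially only with large gaps, such as half of one arm's events lost. These figures rest on the planning rates in section 3.6, an ICC of 0.1, random under-capture and assumed capture fractions.

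**What to change.** Amend sections 3.4 and 5.1 to name one kit-independent source of PrEP initiation and one time window, applied identically in all 44 clusters. Two candidates:

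- PrEP records at the clinics serving the 8 sites, assigned by village of residence or linked to the Manicaland census. The protocol describes no such register, so its content must be checked first.
- A surveillance round in both arms that asks about initiation within the window.

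Linkage should use only identifiers held for both arms, not the names and cell numbers collected for distributors and recipients. Keep kit-label and helpline data for distribution tracking and the process evaluation. Measure self-testing with the same instrument in both arms.

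The cost is a protocol amendment, record abstraction or added survey questions in both arms, and ethics approval for control-area records if not already covered. There will be some linkage error, and men who use clinics outside the sites will be missed; both should be similar between arms if source and identifiers are the same.

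No sample-size figure changes if the source is complete. If it captures 90%, 80% or 70% of initiations equally in both arms, the section 3.6 power calculation with the ICC kept at 0.1 gives 81.6%, 76.7% or 70.7%. Completeness should therefore be assessed when the source is chosen.

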## **5.2 Data management**

Survey data will be entered into and stored within an SQL relational database system. A system is being developed to run validation and internal consistency checks and to generate error reports for immediate follow-up in the field. A dashboard will be created to provide key statistics on recruitment and progress of the study to the investigative and fieldwork management team. Quantitative data will be analysed using standard statistical methods. Qualitative data will be collected in Shona (in the qualitative cohort), transcribed in English and analysed using NUD\*IST.

Unique IDs will be used to identify each participant in the study. The consent audio files will be labelled with the unique ODK generated audio file ID to match with the interview. Audio files will be stored in a password protected standalone local server and encrypted drive and will also be backed up on a separate Imperial College drive. The database will be hosted on the server, owned by Imperial College and located at the field office, with SSL (secure socket layer) and password protected. There will be a local backup database server which is password protected and access rights activated which will not be online. Penetration tests will be contacted on the database servers monthly to ensure that the servers are still safe. Backup files will be hashed and stored in an external drive.

Access to the SQL server database will be limited to the Data Management team only. Requests for data access for analysis purposes will be made to the Data Management team and in such cases, the Data Management team will create pseudonymised datasets, removing any unnecessary personally identifiable for use in data analyses.

## **5.3 Statistical methods for analysing primary and secondary outcomes**

For the test of the intervention effect on the primary and secondary outcomes will be conducted using the intent-to-treat (ITT) analysis for all men randomized at the community level. We will define our intent to treat population as those clusters who were randomized to intervention and control groups. We will use generalized linear models with Poisson distribution, log link function and robust error terms, adjusting for community-level clustering through random effects.

Analysis of baseline data will be carried out once recruitment has completed in all clusters. Final analyses will begin following field data and all associated data cleaning and quality control procedures. No interim analyses will be conducted.

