## **2.3 Trial Design**

The study will use a cluster-randomised trial design with clusters based on existing village boundaries, which have been utilised as part of the ongoing population-based HIV surveillance. In some cases, neighbouring villages will be aggregated to give approximately equal numbers of adult men in each cluster. Feedback from the participatory ‘theory-of-change’ workshops involving key community stakeholders will be taken into account by the PI’s and CoI’s when considering further refinements that can support the successful implementation of the trial. Real-time feedback from the process evaluation will ensure the roll-out is as specified in the protocol thus maximising the fidelity of the intervention.

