### 3.6 Sample size

Based on data on HIV risk collected in the 2020/21 surveillance round we estimate that 33% of men aged 18 and over, will fulfil the requirement for PrEP initiation. A comparable study indicated that 43% of those identified as at risk would take-up PrEP. [18] In the 2020/21 surveillance round 3/3591 (0.14%) men were currently using PrEP. With a continued roll-out of PrEP until the start of the study, we assume a baseline PrEP usage of 1% which will increase to 2% over the course of the trial in control communities. The study will use a cluster-randomised trial design. To have sufficient men in each cluster to explore multiple waves of network recruitment we will create 22 clusters in the intervention arm and 22 in the control, from a total population of 3591 men which equates to 81 men in each cluster. The clusters will be created from either a single village or groups of neighbouring villages. In each intervention cluster a maximum of 90 HIVST kits will be distributed, assuming that 70% of these kits reach men in the cluster, 80% of these men use the HIVST, 33% of these are eligible for PrEP and 43% of these initiate PrEP, we estimate we will have 7.15 men / cluster initiating PrEP a total of 157 men. This represents 8.8% of the study population in the intervention clusters. Using an Intra-Cluster correlation coefficient of 0.1, a conservative estimate based on data collected in similar settings [58] and with a total sample size in the intervention and control arms of 3591 we will have greater than 85 % power to detect a difference in the percentage of men initiating PrEP from 2% in the control arm versus 8.8% in the intervention arm.

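### Section 5.3 names adjustment for clustering only; a cluster-level PrEP-eligible proportion from the 2020/21 surveillance, with the allocation strata, could be pre-specified for a modest gain in precision

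*Protocol*

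**What the plan says.** The primary outcome (section 3.4) is "the proportion of men initiating PrEP out of all men aged 18 and over". Section 5.3 gives the model for primary and secondary outcomes in one sentence: "We will use generalized linear models with Poisson distribution, log link function and robust error terms, adjusting for community-level clustering through random effects". It names no baseline covariate and no stratum term. It does not say that the analysis is unadjusted or that covariates are excluded.

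Three other sections bear on what could be adjusted for:

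- Section 2.3 describes "clusters based on existing village boundaries, which have been utilised as part of the ongoing population-based HIV surveillance".
- Section 3.6 uses the earlier survey to set PrEP need: "Based on data on HIV risk collected in the 2020/21 surveillance round we estimate that 33% of men aged 18 and over" will qualify. The 44 clusters are drawn "from a total population of 3591 men which equates to 81 men in each cluster", and the same 3591 is the denominator for PrEP use in that survey round.
- Section 4.1 stratifies allocation on five socioeconomic settings. Section 5.3 does not carry them into the model.

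No eligibility figure by cluster or by arm is printed anywhere.

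**The concern.** In section 3.6 the eligible share is one of the factors multiplied together to give expected PrEP initiations. If that share varies between clusters, part of the between-cluster variation in the outcome was predictable before randomisation. Left out of the model, that part stays in the standard error, and any chance difference in PrEP need between the arms goes uncorrected.

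Data gathered during the trial cannot fill the gap. Section 5.1 lists recruitment of primary distributors, helpline calls and kit labels. The behavioural risk data of section 3.3.1 come from kit recipients, after allocation and in intervention clusters. Only the surveillance round offers a comparable measure in both arms.

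Naming the covariate in advance matters because section 4.2 says analysts cannot be blinded. A covariate chosen after outcomes are seen would be open to challenge. What is at stake is precision and a modest protection against chance imbalance.

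**Working it through.** **Inputs.** From section 3.6: 22 clusters per arm, 3591 men, ICC 0.1, 2% versus 8.8%, eligible share 33%. Assumed, because not stated: two-sided alpha of 0.05, and the between-cluster SD of the eligible share.

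**1. The plan's own power.** Mean cluster size m = 3591/44 = 81.6. Design effect = 1 + (81.6 − 1) × 0.1 = 9.06. Effective n per arm = 1795.5/9.06 = 198.1. SE of the risk difference = √[(0.02 × 0.98 + 0.088 × 0.912)/198.1] = 2.24 points. Normal-approximation power is Φ(6.8/2.24 − 1.96) = 85.8% with unpooled variance and 85.2% with pooled variance. The stated figure of more than 85% is reproduced without any covariate.

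**2. Where the variance lies.** The between-cluster part is m × ICC = 8.16 of 9.06, or 90%. A cluster-level predictor that explains a fraction R² of it changes the design effect to 0.9 + 8.16 × (1 − R²).

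**3. A plausible R².** The documents give none, so use the plan's own mechanism. If initiation is proportional to the eligible share, the squared coefficient of variation (CV) contributed by that share is (SD/0.33)². The total between-cluster squared CV implied by the ICC is 0.1 × (1 − p)/p. This is a CV of 1.02 at p = 0.088 and 2.21 at p = 0.02. R² is the ratio of the two, computed separately in each arm.

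| Assumed SD of eligible share | R², intervention | R², control | SE (points) | Power, normal |
|---|---|---|---|---|
| 0 | 0 | 0 | 2.24 | 85.8% |
| 5 points | 2.2% | 0.5% | 2.23 | 86.3% |
| 10 points | 8.9% | 1.9% | 2.17 | 88.0% |
| 15 points | 19.9% | 4.2% | 2.07 | 90.8% |

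**4. Cost of estimating the slope.** On a cluster-level t-test, power without a covariate is 84.1% (42 df). One covariate leaves 41 df and inflates the variance by about 1 + 1/40, through chance imbalance in the covariate. Power is then 83.8%, 85.7% or 88.7% at SDs of 5, 10 or 15 points. The gain at 5 points is cancelled. Those at 10 and 15 points shrink to about 1.6 and 4.6 percentage points.

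**5. Adding the strata.** Four stratum terms leave 37 df. If the strata explained nothing at all, power would be 83.5%, 85.4% or 88.5%, a further loss of about 0.2 to 0.3 points. Any variation between settings that they explain is set against that.

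**The case against.** The strongest reply is that section 5.3 is silent rather than restrictive. It gives the model family, link, error type and random effect. A covariate list is ordinary content for a statistical analysis plan, which is not at hand. That stands: the protocol cannot be said to fix an unadjusted primary model.

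A reader might go further and infer that the trial is underpowered or its estimate biased. The documents support neither. The stated power is reproduced without adjustment, and leaving out a prognostic covariate under randomisation does not bias the comparison. The figure does depend on the test: the same inputs give 77.2% on the log risk ratio scale. That difference comes from the scale of the calculation, not from the missing covariate.

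A large gain is also tempting to claim. If the covariate explained 25% or 40% of the between-cluster variance in both arms, power would be about 93% or 97%. Under the proportional mechanism, 40% needs an SD of the eligible share of about 21 points in intervention clusters and 46 points in control clusters. With a mean of 33%, the largest possible SD is √(0.33 × 0.67) = 47 points, reached only if every cluster is at 0% or 100%. Those figures are not credible here.

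Three further limits stand:

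- Section 3.6 itself calls the ICC of 0.1 conservative. At 0.02 the between-cluster share falls to 1.63/(0.98 + 1.63) = 63%, so there is less to gain.
- Stratified allocation already limits imbalance across the five settings. Chance imbalance within strata is what remains.
- The survey predates the November 2023 protocol by about two years or more, and availability by cluster is an inference. If the surveyed men are treated as a sample, a 33% share from 81.6 men has a sampling SE of √(0.33 × 0.67/81.6) = 5.2 points, which would weaken the covariate when true variation is small.

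None of this removes the case for one inexpensive covariate named in advance.

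**Conclusion.** The point holds as a low-cost improvement, not as an error. Section 5.3 names adjustment for clustering alone, while the protocol points to survey data that very likely give a pre-randomisation PrEP-eligible proportion for every cluster in both arms.

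The expected benefit runs from nothing to about 5 percentage points of power, for assumed SDs of the eligible share between 5 and 15 points. It rests on ICC 0.1, on initiation proportional to the eligible share, and on the 2020/21 values still being informative. Adjustment would reduce chance imbalance in PrEP need within strata; it would not remove it.

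**What to change.** Add to section 5.3 that the primary model includes two pre-specified sets of terms: the cluster's proportion of men aged 18 and over who met the PrEP requirement in the 2020/21 round, and the allocation strata of section 4.1, with sparse strata collapsed by a rule set in advance. Entering the proportion on the log scale would match the log link and the multiplicative reasoning of section 3.6. Report the unadjusted estimate as a sensitivity analysis. The same terms can serve the self-testing outcome.

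First confirm that the survey data can be tabulated by trial cluster, and look at the between-cluster SD of the eligible share. This needs no outcome data and shows whether the gain is nearer the 5-point or the 15-point case.

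The cost is a sentence or two in section 5.3, one data extraction, one of 42 between-cluster degrees of freedom for the covariate and up to four for the strata. With 44 clusters, no further cluster-level terms should be added.
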